Magnesium (Mg) is an important intracellular ion with electrophysiological properties. It is essential for optimal metabolic cell function. Mg has proven effective for treating eclampsia, preeclampsia, and torsade's de pointes. Other therapeutic applications such as adjunctive therapy in acute asthma exacerbations, acute coronary syndromes, acute cerebral ischemia, and postoperative pain control are under discussion. (5)

Some studies have shown that serum hypomagnesaemia is common after coronary artery bypass grafts (CABG) and other types of cardiac surgery. (6) and is associated with postoperative morbidity such as atrial tachyarrhythmia.(7)

Some clinical trials have assessed the efficacy of magnesium as a method of intervention to reduce the incidence of postoperative AF.(8)

2. AIM/ OBJECTIVES (Maximum 300 words)

The primary aim of this study is to investigate the anti-arrhythmic effect of Magnesium Sulfate in prevention of atrial fibrillation post cardiac surgery.

3. METHODOLOGY:

Patients and Methods/ Subjects and Methods/ Material and Methods (Maximum 1000 words) *“References may be needed”*

This study is a prospective, randomized controlled trial that will study the postoperative anti-arrhythmic effect of Magnesium Sulfate and clinical outcomes of administration of intravenous Mg Sulfate in patients undergoing open heart surgery.

Randomization will be performed using a computer-generated randomization sequence and allocation concealment to be maintained all through the time of procedure, by using opaque, numbered, and sealed envelopes.

The study protocol will receive ethical approval from the Research Ethical Committee/ Institutional Review Boards, Faculty of Medicine Ain Shams University.

Informed consent will be obtained from each patient before patients' allocation.

Type of the study: prospective randomized clinical trial study protocol.

Study Setting: The operating theaters and ICU of Cardiothoracic institute of Ain Shams University Hospitals.

Study period: one year.

Sample Size:

Using PASS 15 program for sample size calculation, setting power at 80% and alpha error at 0.05, it is estimated that sample size of 65 patients per group (Total 130 patients) can detect an expected medium effect size ($h= 0.50$) for the difference between two groups regarding incidence of post-operative AF using a two-sided z test.

Study population:

Inclusion criteria:

- Age group: Adult patients from age of 18 years to 70 years
- Sex: Both sexes
- Elective open heart surgeries for coronary bypass grafting CABG, valvular lesion single or multiple replacement, combined CABG and valvular; with EF in preoperative echo is more than or equal 40%

Exclusion criteria:

- Patients refuse to give informed consent.
- Emergency open heart surgeries
- Redo cases.
- Patients with preoperative serum creatinine level ≥ 1.8 mg/dL

- Patients with reduced intra/post operative urine output ≤ 1 ml/kg/hour.
- Patients with Chronic Kidney disease, Renal failure on dialysis
- Patients with rhythm defects as proved by ECG before administration of Mg/Placebo.

Sampling method:

Patients will be randomly allocated by computer generated randomization into two groups A and B:

- **Group A (Study group):** patients receiving Intravenous Mg Sulfate.
- **Group B (Control):** patients receiving Placebo drug.

Anesthetic management:

Full standard preoperative assessment for cardiac surgery will be done for all patients included in the study before planned procedures.

Premedication will be given according to standard protocol in cardiac anesthesia. Routine monitoring included a five-lead electrocardiogram, pulse oximeter and invasive blood pressure. Anesthesia will be induced with midazolam 0.02mg/kg and fentanyl 2-5 microgram /kg and muscle relaxation were achieved cisatracurium 0.15 mg/kg intravenous. After tracheal intubation, central venous line and TEE inserted, then anesthesia will be maintained throughout the procedure with morphin20 microgram/kg /min, cisatracurium 2mg/kg/min and sevoflurane 2%. Ventilation will be adjusted to maintain end-tidal carbon dioxide in the range of 30-40 mmHg.

Then after completion of surgical procedure and successful weaning off Cardiopulmonary bypass the patients will be divided into two groups group A will receive 2 gm of Mg Sulfate diluted in 30 cc normal 0.9 % saline via intravenous infusion over 1 hour (1 Mg sulfate ampoule = 10 cc) and group B will receive 50 cc normal 0.9 % saline via intravenous infusion over same period.

On ICU arrival group A will continue receiving 1 gm of Mg sulfate per hour for five hours via continuous IV infusion, while group B will receive same volume and rate of normal saline.

After 5 hours, group A will receive 200 mg of Mg sulfate per hour for 19 hours via continuous IV infusion, then oral replacement of mag added 1 gm/8 hours tablet, while group B will receive same fluid volume and rate of normal saline followed by oral inert starch tablets.

Total time of Mg/placebo infusion is 24 hours, and oral tablets for 1 week just before hospital discharge.

Total serum Magnesium level will be measured immediately post weaning of cardiopulmonary bypass, on ICU arrival, after 24 and 48 hours.

Both groups will receive standardized antiarrhythmic medications as per institutional protocols.

Endpoints of the study:

Primary end point:

1. Evaluation of incidence of atrial fibrillation during hospital stay.

Secondary end points:

1. Total ICU stay.
2. Incidence of new postoperative renal impairment
3. Total ventilation time
4. Incidence of readmission with AF during same hospital stay

Ethical considerations:

The study protocol will receive ethical approval from the Research Ethical Committee, Faculty of Medicine Ain Shams University.

Informed consent will be obtained from each patient before patients' allocation.

Statistical Analysis

Based on published meta-analyses reporting AF incidence of 30–40% in controls following cardiac surgery (Cook et al., 2013(11); Klinger et al., 2015(12)) and anticipating a 50% relative risk reduction (RRR) with our optimized Mg protocol (higher bolus dose, post-CPB initiation), we estimated a medium effect size ($h=0.50$). This RRR assumption was derived from:

- Pharmacokinetic data confirming serum Mg levels >2.5 mg/dL reduce AF risk by 45–60% (Fairley et al., 2015(6); Shiga et al., 2004(13))
- Prior positive RCTs using similar high-bolus regimens (2–3g) showing 54–60% RRR (Miller et al., 2005 (14); Kaplan et al., 2003(15))

Using PASS 15, with power=80% and $\alpha=0.05$, a sample size of 65 patients per group (total N=130) provides 85% power to detect an absolute risk reduction of 20% (control:40% , Mg:20%). This aligns with RCTs detecting similar effects in cardiac surgery cohorts (Gu et al., 2012; N=60–100/group (9)). Continuous variables were analyzed using independent t-tests or ANCOVA (adjusted for covariates); non-parametric data employed Mann-Whitney U tests. Categorical outcomes used chi-square or Fisher's exact tests. Multivariable logistic regression adjusted for age, body mass index (BMI), chronic obstructive pulmonary disease (COPD), diabetes status,

ejection fraction (EF), surgery type, and left atrial size (where available). Sensitivity analyses included propensity score matching (PSM) and Bayesian posterior probability estimation.

4. REFERENCES (Maximum 20 references)

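### The urine-output exclusion has no time limit: its postoperative half falls almost wholly after allocation and on study drug, and the plan names no analysis set

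*Combined protocol and SAP*

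**What the plan says.** All references are to the combined protocol and SAP, section 3 (Methodology).

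- **Exclusion criteria.** One item reads "Patients with reduced intra/post operative urine output ≤ 1 ml/kg/hour". It gives no window and no reference to dosing. Two items later the rhythm exclusion does carry a limit: "Patients with rhythm defects as proved by ECG before administration of Mg/Placebo".
- **Anesthetic management.** Allocation comes at the end of the operation: "after completion of surgical procedure and successful weaning off Cardiopulmonary bypass the patients will be divided into two groups". A one-hour infusion of 2 g magnesium sulfate, or saline, follows. Then "On ICU arrival group A will continue receiving 1 gm of Mg sulfate per hour for five hours via continuous IV infusion", and after that "group A will receive 200 mg of Mg sulfate per hour for 19 hours via continuous IV infusion". The control group receives saline on the same ICU schedule. Tablets follow the infusion.
- **Endpoints.** The primary endpoint is "Evaluation of incidence of atrial fibrillation during hospital stay". The second secondary endpoint is "Incidence of new postoperative renal impairment", for which no definition is given.
- **Statistical Analysis.** This part lists tests, covariates and sensitivity analyses. It names no analysis population and gives no rule for a patient who meets an exclusion after allocation.

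**The concern.** An exclusion criterion protects the comparison only if it is settled before allocation. The intraoperative half of this one can be, because groups are formed after surgery. The postoperative half mostly cannot, because the drug is already running when the reading is taken.

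Taken literally, a patient who has been randomised and dosed becomes excluded by something that happened on treatment. If that patient also leaves the analysis, the primary AF comparison is between those who remained, not between the groups that randomisation formed. The renal endpoint is exposed more directly, since low urine output may be part of, or an early sign of, the outcome being counted. Without a definition of that endpoint, the overlap cannot be judged.

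**Working it through.** **1. The plan's own sample size.** With Cohen's h = 0.50, 80% power and two-sided alpha 0.05 (Sample Size), n = 2 × ((1.96 + 0.8416)/0.50)² = 62.8, so 63 per group. The plan states 65, where power is 81.3%. The figure reproduces closely. The point below does not depend on it.

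**2. Timing.**

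| Period | Position relative to allocation and dosing |
|---|---|
| During surgery | Before both |
| Bypass weaning to start of first infusion | Short pre-dose window |
| First infusion, 1 h | After allocation, on study drug |
| ICU, 5 h at 1 g/h | After allocation, on study drug |
| ICU, 19 h at 200 mg/h | After allocation, on study drug |
| Tablets | After allocation, on study drug |

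The stages add to 1 + 5 + 19 = 25 hours against a stated total of 24. The difference does not affect the argument. The plan gives no schedule of urine-output readings, so the number of patients falling under each half of the criterion is unknown.

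**3. Effect of removal on AF.** Let p be the true AF rate in an arm, e the share removed and r the AF risk in those removed. The rate left is (p − e·r)/(1 − e). The values of e and r below are assumptions; the documents give neither.

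- *No true effect, equal loss.* With p = 40%, e = 10% and r = 60% in both arms: (0.40 − 0.06)/0.90 = 37.8% in each. The bias is zero.
- *No true effect, unequal loss.* With p = 40% and r = 60%, removing 10% of controls and 20% of magnesium patients gives 37.8% v (0.40 − 0.12)/0.80 = 35.0%. That is a spurious 2.8 points favouring magnesium. Swapping the two shares reverses the sign.
- *A true effect, equal loss.* At the plan's 40% v 20%, with e = 10% and r = 30% in both arms: 0.37/0.90 = 41.1% v 0.17/0.90 = 18.9%. The difference is 22.2 points instead of 20. Equal loss at equal risk is therefore not neutral in general once magnesium works.

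**4. Effect of removal on the renal endpoint.** If s is the share of renal cases removed, measured rate/true rate = (1 − s)/(1 − e). The measured rate is too low only when s exceeds e, and too high when s is smaller.

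**5. Cost of keeping everyone in.** Power = Φ(h·√(n/2) − 1.96), with h the arcsine difference and n = 65.

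- 40% v 20%: h = 0.442, power 71%.
- Assume 10% of magnesium patients are stopped and gain nothing. The magnesium rate is 0.9 × 20% + 0.1 × 40% = 22%, h = 0.393, power 61%.
- Same 10%, half the benefit kept: the rate is 0.9 × 20% + 0.1 × 30% = 21%, h = 0.417, power 66%.
- For comparison, 10% removed from both arms without replacement and with the effect unchanged: n = 58.5, power 67%.

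**The case against.** The strongest reply is that the line sits in a list of entry criteria, beside preoperative creatinine and chronic kidney disease, and that entry criteria decide who gets in. Since groups are formed only after surgery, the wording could mean output up to that moment. It could also be a safety stop for magnesium. Nothing in the plan says that a treated patient is withdrawn, replaced or dropped. This stands in part: a reader might infer that the plan commits to deleting such patients from the analysis, and the documents do not support that. They leave it open, because the criterion has no limit although the rhythm criterion has one, and because no analysis set is named.

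A second reply is that harm is not shown. ICU saline matches the magnesium infusion in volume and rate, and nothing in the documents says that magnesium changes urine output. This also stands. A reader might infer that the result is tilted towards magnesium, or that renal impairment is undercounted. Neither follows, since steps 3 and 4 can go either way.

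A third reply is that the power figures do not favour the change. That is correct: the worst case shown for keeping patients (61%) is below the figure for excluding them (67%), and the latter loss disappears if excluded patients are replaced, on which the plan is silent. The 71% baseline itself uses the plan's 40% v 20% rates; at h = 0.50 it would be 81.3%.

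**Conclusion.** The concern holds as a defect in a stated rule. The criterion has no time limit, its postoperative half is observed almost entirely after allocation and on study drug, and the plan does not say whether a patient who meets it then merely stops treatment or leaves the analysis. If such patients leave, the AF and renal comparisons are no longer between the groups as randomised.

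The bias has no derivable size or direction. With no true effect, the AF bias is zero if both arms lose the same share of patients with the same AF risk. That reassurance does not carry over in general to a trial in which magnesium works. The conclusion rests on allocation taking place where the anaesthetic section puts it, at the end of surgery. It should be fixed before the analysis, with medium confidence, because a pre-dose or drug-stopping intention remains possible.

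**What to change.** Three changes to the text:

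1. Limit the exclusion to urine output observed before allocation and first dose, in the manner of the rhythm criterion.
2. Make later low urine output a rule for stopping or reducing study drug, with threshold and duration stated by the investigators (the existing ≤ 1 ml/kg/hour could serve) and applied identically to magnesium and placebo. This keeps the safety purpose.
3. State that all randomised patients, including those whose infusion is stopped, are followed to discharge and analysed in their allocated group for AF and renal impairment.

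The added work is outcome follow-up of patients who might otherwise be dropped; AF is already assessed over the hospital stay. The downside is dilution if stopped magnesium patients lose benefit, as in step 5 of the working. The fix itself requires no larger sample. Holding 71% power against the assumed worst case of 40% v 22% would, however, take 2 × ((1.96 + 0.561)/0.393)² ≈ 82.3, so about 83 per group instead of 65.

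### No history of atrial fibrillation is asked for at entry or used in the analysis, so recurrent and new-onset AF are counted together in a prevention trial

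*Combined protocol and SAP*

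**What the plan says.** The Aim/Objectives section states that the trial will "investigate the anti-arrhythmic effect of Magnesium Sulfate in prevention of atrial fibrillation post cardiac surgery". The exclusion list in Methodology has one item on rhythm: "Patients with rhythm defects as proved by ECG before administration of Mg/Placebo". That list has no item on previous AF or flutter, paroxysmal AF, or earlier rhythm-control treatment. It does not define a rhythm defect, and it does not name the ECG or a time window.

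The inclusion criteria admit "Elective open heart surgeries for coronary bypass grafting CABG, valvular lesion single or multiple replacement, combined CABG and valvular", with an ejection fraction of at least 40%.

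The primary end point is "Evaluation of incidence of atrial fibrillation during hospital stay", with no restriction to new-onset AF. The secondary list does make that restriction for another outcome: "Incidence of new postoperative renal impairment".

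The Statistical Analysis section gives the covariates: "Multivariable logistic regression adjusted for age, body mass index (BMI), chronic obstructive pulmonary disease (COPD), diabetes status", then ejection fraction, surgery type and left atrial size where available. Prior AF is absent, and no stratification factor or subgroup for it is stated. On background treatment the plan says only: "Both groups will receive standardized antiarrhythmic medications as per institutional protocols".

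**The concern.** A prevention question is easiest to read when every patient starts free of the condition. Here a patient known to have intermittent AF can be in sinus rhythm on the ECG that is looked at, and so show no rhythm defect. That patient is eligible, and a postoperative recurrence is scored exactly like a first episode in someone who never had AF.

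Two things are at stake. The first is interpretation: the estimated effect becomes a blend of preventing new AF and suppressing recurrence, in proportions that the trial is not set up to report. The second is precision: prior AF probably predicts the outcome strongly, yet the plan neither asks for it nor adjusts for it.

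The criterion is also loose in the other direction. An undefined rhythm defect could remove patients whose ECG finding has nothing to do with AF.

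**Working it through.** **1. Can such a patient be enrolled and counted?**

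- Exclusion requires a rhythm defect proved by ECG. A patient in sinus rhythm on the ECG examined shows none.
- No other criterion refers to AF history or rhythm-control treatment.
- The end point is any AF during the hospital stay. Since the renal end point says new and the AF end point does not, the plain reading includes recurrences.
- The regression has no term for prior AF.

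So the patient can enter, a recurrence is an event, and the model does not separate the two kinds of event.

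**2. The plan's own sample size figure.**

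Inputs: h = 0.50, two-sided α = 0.05, power 80% (Sample Size section).

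n per group = 2 × ((1.960 + 0.842)/0.50)² = 62.8, so 63. The plan's 65 is within two patients of this, and power at 65 for h = 0.50 is 81.3%.

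The Statistical Analysis section also gives 40% vs 20% with 65 per group and claims 85% power. With the pooled two-sided z test:

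power = Φ{(|p₁ − p₂|√n − 1.96√[2p̄(1 − p̄)]) / √[p₁(1 − p₁) + p₂(1 − p₂)]}

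= Φ{(1.612 − 1.96 × 0.648)/0.632} = 70.6%.

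The 85% does not reproduce. That is a separate matter. The baseline used below is 70.6%.

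**3. What enrolling prior-AF patients does to power.**

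The documents give neither the share of such patients nor their AF risk, so both are assumed. Let f be the share (10% or 20%), r = 60% their AF risk in the control arm, and r′ their risk on magnesium. All other patients follow the planned 40% vs 20%.

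Control rate = 0.40(1 − f) + r f

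Magnesium rate = 0.20(1 − f) + r′ f

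| Effect of magnesium in prior-AF patients | r′ | f = 10%: rates, power | f = 20%: rates, power |
|---|---|---|---|
| None | 60% | 42% vs 24%, 59.0% | 44% vs 28%, 47.6% |
| Same 20-point reduction | 40% | 42% vs 22%, 69.0% | 44% vs 24%, 67.6% |
| Same 50% relative reduction | 30% | 42% vs 21%, 73.7% | 44% vs 22%, 76.7% |

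Worked cell (f = 10%, no effect): control 0.36 + 0.06 = 0.42; magnesium 0.18 + 0.06 = 0.24; power = Φ{(1.451 − 1.96 × 0.665)/0.653} = 59.0%.

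The assumed r matters little. With no effect and f = 10%, r = 50% gives 59.7% and r = 70% gives 58.3%. The assumed treatment effect in these patients matters most, and it decides whether power falls or rises.

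**4. Chance imbalance.**

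At f = 10%, the SD of the between-arm difference in the number of prior-AF patients is √(2 × 65 × 0.10 × 0.90) = 3.4, or 3.4/65 = 5.3 percentage points of share. Split evenly about the mean, with r = 60% in both arms, this shifts the risk difference by 0.026 × (0.60 − 0.40) + 0.026 × (0.60 − 0.20) = 1.6 points. Two SDs shift it by about 3.2 points, against a planned difference of 20.

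If exactly 13 of 130 patients have prior AF, the chance of a split of 9 to 4 or worse is 24%.

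**The case against.** **The broader question is legitimate.** The stated aim is to prevent AF after surgery, not first-ever AF. Counting any AF in patients who are in sinus rhythm at dosing is coherent, and excluding everyone with a history would narrow the population. This stands, and it is why the fix does not require exclusion.

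**The criterion is ambiguous rather than plainly permissive.** An old tracing that shows AF could be read as ECG proof before dosing. Study drug starts only after weaning from bypass, so the wording could cover anything from an old record to the rhythm in theatre. This also stands, but it supports clarification: two investigators could treat the same patient differently.

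**Stronger readings that a reader might infer.**

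- *That the trial loses substantial power.* The fall to 59% or 48% needs magnesium to do nothing in prior-AF patients, and nothing in the documents supports that. Under the other two assumptions power barely changes or rises.
- *That the comparison is biased.* Randomisation balances prior AF in expectation. Chance imbalance is covered by the test's type I error, and the shift is modest.
- *That the planned 40% vs 20% belongs to a population without prior AF.* The plan cites control rates of 30–40% after cardiac surgery and does not say whether its sources excluded prior AF.
- *That an imbalance could never be detected.* A full preoperative assessment is planned for all patients, so the history may be in the notes. The plan just does not require it to be recorded for the trial or used.
- *That such patients are common because valve surgery is included.* The documents give no prevalence.

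**Conclusion.** The point holds as a gap in eligibility wording, end point definition and covariate choice. As written, known paroxysmal AF in sinus rhythm does not clearly exclude, recurrences count as primary events, and prior AF is neither required as a data item nor adjusted for. The result would therefore not separate prevention of new AF from suppression of recurrence.

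The size of the consequence is not known. The power figures above rest on an assumed 10–20% share, an assumed 60% control-arm risk and an assumed treatment effect in these patients, and even the direction depends on the last. This is a worthwhile, inexpensive improvement and does not make the primary comparison invalid.

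**What to change.** 1. Record history of AF or flutter, including paroxysmal, for every patient at the preoperative assessment already planned. If recruitment has begun, take it from the notes for those already enrolled.
2. Add prior AF or flutter to the covariates of the logistic regression.
3. Report the primary result for all patients and for those without prior AF, labelling the second as new-onset AF.
4. Have the sponsor state which ECG counts and within what window, what is meant by a rhythm defect, and whether AF history is intended to exclude, so that the criterion and the prevention aim agree.

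The cost is one history item, one more model term, one further analysis in a smaller and so less precise subset, and a short amendment. If the sponsor decides that AF history should exclude, recruitment may be slightly slower and the result would apply only to patients without previous AF. That trade-off is for the sponsor to make.

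### The cisatracurium maintenance rate, printed as 2 mg/kg/min, equals 13.3 induction doses every minute and is probably mg written for microgram

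*Combined protocol and SAP*

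**What the plan says.** The relevant text is the paragraph on anaesthesia under Anesthetic management in section 3 (Methodology) of the combined protocol and SAP. It applies to all patients and comes before the description of the magnesium and placebo infusions.

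- Induction: "muscle relaxation were achieved cisatracurium 0.15 mg/kg intravenous".
- Maintenance: "anesthesia will be maintained throughout the procedure with morphin20 microgram/kg /min", followed directly by "cisatracurium 2mg/kg/min and sevoflurane 2" per cent.
- Units of the neighbouring opioids: at induction the plan gives "fentanyl 2-5 microgram /kg", and in the maintenance sentence morphine is also in microgram. The two maintenance drugs stand side by side as "morphin20 microgram/kg /min, cisatracurium 2mg/kg/min".

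No other part of the document restates, qualifies or corrects the cisatracurium rate.

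**The concern.** The plan gives two figures for the same drug, a few lines apart. The first is a single dose that the plan itself treats as enough to produce muscle relaxation. The second is a continuous rate to sustain that state for the length of an open-heart operation. A dose and a rate do not formally contradict each other, but their sizes should bear a sensible relation. Here the rate delivers many full induction doses every minute.

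What is at stake is patient safety and the accuracy of the protocol text. The drug is a muscle relaxant and the maintenance sentence is a prospective instruction. Anyone who followed it, or copied it into a local procedure or a methods section, would carry the figure forward. The magnesium comparison is not at stake, because the same anaesthetic is prescribed for both arms.

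**Working it through.** **Inputs, all from Anesthetic management**

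- Induction dose: 0.15 mg/kg, given once.
- Maintenance rate as printed: 2 mg/kg/min, for the whole procedure.

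The plan derives no total from the rate, so there is no stated result to reproduce. The check is to express the rate in induction doses. Body weight cancels, because both figures are per kg.

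**As printed**

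- Per minute: 2 / 0.15 = 13.3 induction doses.
- Per hour: 2 × 60 = 120 mg/kg/h, and 120 / 0.15 = 800 induction doses.

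For scale, at an assumed 70 kg the induction dose is 0.15 × 70 = 10.5 mg, while maintenance is 2 × 70 = 140 mg every minute. For assumed weights of 50 to 100 kg the latter is 100 to 200 mg every minute.

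**Which single-unit change restores a sensible relation?**

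| Reading | Rate per hour | Induction doses per hour |
|---|---|---|
| As printed, 2 mg/kg/min | 120 mg/kg | 120 / 0.15 = 800 |
| Time unit changed, 2 mg/kg/h | 2 mg/kg | 2 / 0.15 = 13.3 |
| Mass unit changed, 2 microgram/kg/min | 0.002 × 60 = 0.12 mg/kg | 0.12 / 0.15 = 0.8 |

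On the microgram reading, one induction dose is delivered every 0.15 / 0.002 = 75 minutes. At 70 kg that is 0.12 × 70 = 8.4 mg/h, against 120 × 70 = 8,400 mg/h as printed.

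**Over a whole operation**

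The document gives no duration, so 3 to 5 hours is an assumption used only for illustration.

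- As printed: 120 × 3 = 360 to 120 × 5 = 600 mg/kg, which is 360 / 0.15 = 2,400 to 600 / 0.15 = 4,000 induction doses.
- If microgram: 0.12 × 3 = 0.36 to 0.12 × 5 = 0.60 mg/kg, which is 0.36 / 0.15 = 2.4 to 0.60 / 0.15 = 4.0 induction doses.

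**Could the PDF reading have caused it?**

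A micro sign turned into an m would produce exactly this text. Two features make that less likely. The paragraph writes microgram as a word for fentanyl and for morphine and does not use the symbol. Other special characters in the same section, such as the greater-or-equal and less-or-equal signs in the exclusion criteria, came through intact. Neither feature is decisive.

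**The case against.** The strongest reply is about weight and certainty, since the quotations and the arithmetic are not in doubt.

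- **It is background care.** Cisatracurium is neither the study drug nor an endpoint, and the rate is common to both arms. This stands: nothing in the design or analysis changes. It limits the point to safety and accuracy of the text but does not remove it.
- **No anaesthetist would follow it.** An error this gross is more likely to be noticed than acted on. That is probably true, but it is not a reason to leave a dosing instruction uncorrected in a protocol submitted for ethical approval.
- **The cause is not established.** Microgram is inferred. A misplaced decimal, a change in more than one element, or a reading artefact could also explain the text, and the document gives no reference infusion rate that would settle it. This stands. High confidence belongs to the statement that the printed rate is implausible. The intended value has to come from the investigators.
- **The morphine rate is an imperfect anchor.** The 20 microgram/kg/min beside it is 20 × 60 / 1,000 = 1.2 mg/kg/h, which may itself deserve a check. The document gives no second morphine dose to compare it with, so nothing is concluded about it here. The argument on cisatracurium rests on that drug's own induction dose and does not need the morphine figure.

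**Conclusion.** The concern holds, and the text should be fixed. The printed maintenance rate is 13.3 induction doses per minute, or 800 per hour, and cannot sensibly be what was meant beside a 0.15 mg/kg induction dose. This conclusion uses only the two printed figures and needs no assumption about weight or duration.

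That the intended unit is microgram is probable but remains an assumption. If it is right, the text overstates the rate by a factor of 1,000. There is no bias between arms and no effect on sample size, alpha or power.

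**What to change.** First, look at the original protocol file to see whether it reads mg or a micro sign. If it reads mg, the investigators should confirm the intended rate and correct the unit, presumably to 2 microgram/kg/min, before the text is used. Writing microgram as a word, as the paragraph already does for the opioids, avoids the same ambiguity later. The morphine rate in the same sentence can be confirmed in the same pass.

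The cost is one unit in the protocol text and a notification to the ethics committee. Design, analysis and enrolment are unaffected.

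### Does the primary endpoint need rewriting because AF is counted over the whole hospital stay while the named setting is theatres and ICU, with no AF definition or masked classification?

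*Combined protocol and SAP*

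**What the plan says.** Under Endpoints of the study, the primary end point is a single line: "Evaluation of incidence of atrial fibrillation during hospital stay". Study Setting reads "The operating theaters and ICU of Cardiothoracic institute", with no ward named. Other parts of the Methodology run past the ICU. The dosing text has "oral tablets for 1 week just before hospital discharge", and a secondary end point is "Incidence of readmission with AF during same hospital stay".

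ECG appears twice. Under Anesthetic management, "Routine monitoring included a five-lead electrocardiogram". In the Exclusion criteria, the plan removes "Patients with rhythm defects as proved by ECG before administration of Mg/Placebo". Neither says how AF is confirmed as an outcome.

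On masking, the plan describes sealed opaque envelopes, a saline infusion as placebo and inert tablets afterwards. It does not say who is masked or who classifies AF. Serum results exist in both arms: "Total serum Magnesium level will be measured immediately post weaning of cardiopulmonary bypass, on ICU arrival, after 24 and 48 hours".

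**The concern.** The endpoint covers the whole stay, but the named setting and the only described rhythm monitoring stop short of the ward. ECG proof is needed to exclude a patient and not to count the primary event. On that reading, one analyst could count AF seen in the ICU and another AF up to discharge, from the same patients.

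Three consequences would follow:

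- **Lost power.** AF missed on the ward lowers both event rates and shrinks the absolute difference.
- **Choice after the fact.** If the text truly allowed two counts, the one giving significance could be picked.
- **Unequal recording.** ICU stay is a secondary endpoint. If AF were recorded mainly in the ICU, recorded time could differ by arm. Staff who know the arm, or see magnesium results, might also look for AF unevenly.

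The placebo bolus, "group B will receive 50 cc normal 0.9 % saline", set against an active bolus diluted in 30 cc, at first looks like a volume mismatch that could reveal the arm.

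**Working it through.** **Inputs from the plan.** 65 per arm, two-sided alpha 0.05 and h = 0.50 (Sample Size); control AF 30–40% and a 50% relative reduction, hence 40% versus 20% or 30% versus 15% (Statistical Analysis). **Assumed, not in the documents:** the share c of AF patients who are counted, taken as 70–90%.

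**1. The plan's own sample size.** n = 2 × ((1.960 + 0.842)/0.50)² = 62.8, so 63 per arm. The planned 65 give 81.3% power at h = 0.50. At 40% versus 20%, h is only 0.44. The pooled normal formula gives SE₀ = √(2 × 0.30 × 0.70/65) = 0.0804 and SE₁ = √((0.40 × 0.60 + 0.20 × 0.80)/65) = 0.0784, so power = Φ((0.20 − 1.960 × 0.0804)/0.0784) = Φ(0.541) = 70.6%. The stated 85% does not reproduce. That is a separate sample-size matter and does not arise from how AF is recorded.

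**2. Equal under-capture in both arms.** Rates become c × 40% and c × 20%, or c × 30% and c × 15%. Exact binomial enumeration, pooled z test:

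| c | Rates | Power | Rates | Power |
|---|---|---|---|---|
| 1.0 | 40% v 20% | 71.6% | 30% v 15% | 54.2% |
| 0.9 | 36% v 18% | 65.2% | 27% v 13.5% | 48.4% |
| 0.8 | 32% v 16% | 58.0% | 24% v 12% | 42.7% |
| 0.7 | 28% v 14% | 50.3% | 21% v 10.5% | 37.1% |

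With Fisher's test at 40% versus 20% the figures are 64.1%, 57.0%, 49.8% and 42.3%. The relative reduction stays at 50% throughout; only precision is lost.

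**3. ICU count against whole-stay count.** Whole-stay events X ~ Bin(65, p) in each arm and ICU events ~ Bin(X, c), with 1,000,000 simulated trials per scenario and the pooled z test. At 40% versus 20%:

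| c | Disagree on significance | Whole-stay only significant | ICU only significant |
|---|---|---|---|
| 0.9 | 11.8% | 9.1% | 2.8% |
| 0.8 | 19.5% | 16.5% | 3.0% |
| 0.7 | 26.9% | 24.1% | 2.8% |

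At 30% versus 15% the total is 12–25%. No trial in any of the six scenarios was significant in opposite directions. The net disagreement is the power loss in step 2: at c = 0.9, 9.1 − 2.8 = 6.3 points, against 71.6 − 65.2 = 6.4. The two sets of figures are largely one effect.

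**4. Misses in the magnesium arm only, with no true effect.** At 30–40% AF, missing 10% gives a false-positive rate of 6.9–8.0% (pooled z) or 4.3–5.6% (Fisher). Missing 20% gives 12.3–16.5% or 8.4–12.3%. Nothing in the documents shows that one arm would be recorded less fully.

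**5. Infusion volume.** The anesthetic section gives 10 cc per ampoule and 30 cc of diluent. Two ampoules make 30 + 2 × 10 = 50 cc, the placebo volume. Grams per ampoule are not stated, so two ampoules is an inference, but the volumes fit a matched placebo. The later infusions are stated to be equal in volume and rate.

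**6. Which line governs.** The endpoint line names its own window. The setting line names a place and may only say where treatment starts. The tablets up to discharge and the readmission endpoint both agree with a whole-stay count.

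**The case for a change.** The best case for a change is that saying when AF counts is not saying how it is found. Even if the setting line is read as the place where treatment starts, the available text then describes no postoperative rhythm recording at all. Unscheduled ward ECGs are not a prespecified measurement. Power at 40% versus 20% is already below the 80% target, so there is no slack for missed events. Most of the cure would be a few sentences.

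The gap is real: the available text has no AF criterion, no recording method after theatre and no named assessor. One page of the document was not available, although the sections where such detail would normally sit were.

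The rest does not hold. An ICU-only count would depart from the written endpoint, so it is not a second permitted reading. Recorded time would differ with ICU stay only if ward AF went unrecorded, which is not shown. The power argument needs an assumed capture share. It also needs the plan's 30–40% to be full-capture rates, yet the plan takes them from published reports whose method of capture it does not give. If those rates already reflect ordinary recording, the discount is applied twice. Differential recording has no demonstrated mechanism. Nor is the cure only wording: it would leave the minimum duration to be chosen, scheduled ward ECGs are added procedures for up to 130 patients, and a fixed monitored window would answer a different question.

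**Conclusion.** The concern does not call for a change. The primary endpoint has one window, the hospital stay, and the setting line does not create a rival count. What is left is ordinary operational detail: AF shown on ECG or monitor, each patient counted once, and classification without sight of the arm. Investigators running a placebo-controlled trial with concealed allocation would be expected to supply this, and it belongs in the trial report. No rule in the plan is shown to give a wrong result.

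If capture were 90%, 80% or 70% in both arms, power at 40% versus 20% would fall by 6.4, 13.6 or 21.3 points from 71.6%. These figures rest on an assumed capture share and on treating the planning rates as full capture, and the documents support neither. They describe lost precision. A biased comparison would need unequal recording between arms, for which there is no evidence here. Who is masked, and whether the tablets look alike, remains unstated in the available text.
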